Baseline risk factors for ILD will be measured including: age, sex, history of pneumonia, chronic obstructive pulmonary disease, chronic kidney disease, hepatitis C, history of tuberculosis sarcoidosis, history of autoimmune diseases, history of connective tissue disorders, history of sarcoidosis, history of cancer, exposure to medications (nitrofurantoin, sulfonamides, amiodarone, methotrexate, cyclophosphamide, dronedarone, SSRIs/SNRI antidepressants, anticonvulsants, antiplatelets, statins, angiotensin converting enzyme inhibitors (ACEI), angiotensin-II receptor blockers (ARB), thiazide diuretics and systemic fluoroquinolone antibiotics [Detailed list is shown in Annex 2]), smoking status. [9, 10] Smoking status may be missing. We will include current smoking status as a binary variable. An individual will be classed as a current smoker (1) or non-current smoker (0, i.e., other smoking status or the absence of a smoking status) based on the most recent smoking status prior to their index date. Risk factors that will not be reliably identifiable include environment and occupational exposures, family history, and biologics, and will not be considered in the analysis. Information on prior radiotherapy and chemotherapy may not be available for some patients but will be included in the analysis when available.

Additionally, the incidence of ILD has changed substantially over time as well as the prescription patterns of the exposures. We will therefore also account for calendar year in the propensity score analysis.

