5.6.2. Main statistical methods

Propensity score matching will be performed using a 1:1 matching of warfarin users to DOAC users using a caliper width of 0.2 of the standard deviation of the logit of the propensity score. [11] We will include the baseline risk factors and calendar year as predictor variables in the propensity score. Matching will occur by indication (AF and VTE). Absolute standardised mean differences (SMD) for each variable will be calculated before and after propensity score matching, with SMD of less than 0.1 representing successful matching. We will visually check the distributions of the propensity scores across treatment arms, within strata (indication, database). If the sample size appears insufficient after matching, we will use Inverse Probability Treatment Weighting (IPTW) instead of matching.

In the propensity-matched cohort, the incidence of each study outcome will be estimated between target (DOAC) and comparator (warfarin) groups. Cox models will be used to calculate hazard ratios for the instantaneous risk of the ILD outcome. Where death is available in the data source, competing

mortality risk will be accounted for by estimating cause-specific hazard functions. We will apply two analytical approaches: an **on-treatment analysis** (OT) and an **intention to treat analysis** (ITT as per the study by Chan et al.).

Summary of key analysis factors:

- 4 Countries
- 4 DOACs + 1x all DOACS = 5 (warfarin is comparator)
- 2 indications

This brings the number of analyses to $4 * 5 * 2 = 40$ (this number will vary depending on the analytical approach and principal findings).

5.6.3. **Meta-analysis**

Hazard ratios will be reported for each database, exposure and indication separately. Log hazard ratios will also be meta-analysed across databases using a random-effects model using REML (Restricted Maximum Likelihood). 95% Confidence intervals will be provided using the HKSJ method. [12, 13] 95% approximate prediction intervals will be provided. [14] I^2 will be estimated to describe the percentage of the variability in effect estimates that is due to heterogeneity rather than sampling error.

5.6.4. **Missing data**

The analysis will be conducted on the assumption that an individual has a condition or prescription exposure if it is recorded in their electronic health record. No multiple imputation methods will be performed. Therefore, patients with missing records for an indication will be excluded from the analyses.

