5.8. Limitations of the research methods

Limitations of this study include the potential for missing data if exposure, outcomes, or covariates are not recorded in an individual's electronic health record. Only primary care databases will be used with no linkage to hospital diagnoses that could lead to under ascertainment of outcomes.

Known risk factors for ILD are used as covariates to estimate the propensity score. However, some risk factors will not be possible to include (e.g., environmental exposure) and unknown risk factors may remain. The analysis will control for baseline observed confounders. Complex time-varying analysis of confounders (e.g., drug exposure) will not be performed. Thus, residual confounding remains possible.

Diagnostic coding for ILD is not known to have been validated in the primary care databases available. Although confirmation of the diagnoses requires specialist input, the nature of the diagnosis means that its recording in primary care records could be reasonably accurate. However, this assumption should be treated cautiously. We will assess narrow and broad definitions in the analyses to account for uncertainties around potential misclassification of ILD.

For privacy of the patients, the exact dates of birth and death are not recorded in the used databases. Instead, year of birth is available, and for patients whose death is registered, year of death is available. This increases the estimates for exposure time.

6. Protection of human subjects

Patient confidentiality will be protected according to the EU General Data Protection Regulation (GDPR) on the protection of individuals.

7. Management and reporting of adverse events/adverse reactions

Pursuant to the requirements for reporting of adverse events for secondary data (GVP module VI, VI.C.1.2.1.2), adverse event reporting will not be conducted as part of this study given the study objectives will be met through the use of secondary data.

8. Plans for disseminating and communicating study results

The analysis plan and study results will be published in EUPAS registries upon completion.

9. References

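### Heart failure is not a named covariate, so it is neither directly matched on nor balance-checked, although in AF it may affect both anticoagulant choice and the chance of an ILD code

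*Protocol*

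**What the plan says.** Protocol 5.5 (Other variables) opens the covariate list with "Baseline risk factors for ILD will be measured including: age, sex, history of pneumonia, chronic obstructive pulmonary disease, chronic kidney disease, hepatitis C". It continues with tuberculosis and "history of autoimmune diseases, history of connective tissue disorders, history of sarcoidosis, history of cancer", then medicines. These include amiodarone, dronedarone, antiplatelets and statins, and the cardiovascular part ends with "angiotensin converting enzyme inhibitors (ACEI), angiotensin-II receptor blockers (ARB), thiazide diuretics and systemic fluoroquinolone antibiotics". Current smoking is also included. The same section names the risk factors that cannot be identified reliably: environmental and occupational exposures, family history and biologics. Heart failure is in neither group and appears nowhere in the readable text. Loop diuretics are not named either.

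Section 5.6.2 then states: "We will include the baseline risk factors and calendar year as predictor variables in the propensity score". Its rule for judging the match reads "Absolute standardised mean differences (SMD) for each variable will be calculated before and after propensity score matching, with SMD of less than 0.1 representing successful" (the quote stops one word before the end of the sentence).

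On the outcome, 5.8 says "Diagnostic coding for ILD is not known to have been validated in the primary care databases available" and offers this in mitigation: "We will assess narrow and broad definitions in the analyses to account for uncertainties around potential misclassification of ILD". On confounding, it accepts that "some risk factors will not be possible to include (e.g., environmental exposure) and unknown risk factors may remain".

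**The concern.** The covariates are chosen as risk factors for having ILD. The outcome that is analysed is a recorded ILD code in primary care, without linkage to hospital diagnoses. Such a code depends on who has the disease and also on who is examined, imaged and referred. In an AF cohort, heart failure is a plausible reason for breathlessness and chest work-up, so it can plausibly raise the chance of an ILD code, whether the code is correct or not. It can also plausibly bear on which anticoagulant is started. A variable with both links is a confounder of the recorded outcome even if it does not cause ILD.

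A rule that selects known ILD risk factors would not pick it up, and no feasibility reason is given for leaving it out. If the arms still differed in heart failure after matching, every listed covariate could meet the 0.1 limit and the hazard ratio would still carry the difference. If the imbalance ran the same way in all four databases, the meta-analysis would not remove it and the confidence interval would not reflect it.

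**Working it through.** The protocol states no heart failure prevalence, event count or sample size, so there is no figure of its own to reproduce. The check has two parts.

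**1. What the plan does with heart failure.**
- 5.5: not on the covariate list, and not among the factors declared not identifiable.
- 5.6.2: the propensity score takes the listed risk factors and calendar year. The SMD is calculated for each variable, which is naturally read as each covariate.
- Result: as written, heart failure is balanced only as far as the listed drugs and conditions track it, and no one sees how far that is.

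**2. How large the effect could be.** All inputs below are assumptions. Let p(DOAC) and p(VKA) be the heart failure prevalence in each arm after matching on the current list, and RR the relative risk of a recorded ILD code with versus without heart failure.

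Bias factor on the hazard ratio = [1 + p(DOAC)(RR − 1)] / [1 + p(VKA)(RR − 1)]

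SMD = |p(DOAC) − p(VKA)| / √{[p(DOAC)(1 − p(DOAC)) + p(VKA)(1 − p(VKA))] / 2}

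| p(DOAC) | p(VKA) | SMD | RR | Bias factor |
|---|---|---|---|---|
| 20% | 25% | 0.05/0.417 = 0.12 | 1.5 | 1.10/1.125 = 0.98 |
| 20% | 30% | 0.10/0.430 = 0.23 | 2 | 1.20/1.30 = 0.92 |
| 20% | 30% | 0.23 | 2.5 | 1.30/1.45 = 0.90 |
| 25% | 20% | 0.12 | 1.5 | 1.125/1.10 = 1.02 |
| 30% | 20% | 0.23 | 2 | 1.30/1.20 = 1.08 |
| 30% | 20% | 0.23 | 2.5 | 1.45/1.30 = 1.12 |

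Both assumed imbalances exceed the protocol's 0.1 limit, but with heart failure off the list neither SMD would be calculated. A bias of more than 15% needs stronger inputs, for example 20% versus 35% with RR 3 (1.40/1.70 = 0.82).

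**After the fix.** With equal prevalence the factor is 1.00. If heart failure only just passes the rule (20% versus 24%, SMD 0.04/0.414 = 0.097), the factor is 1.10/1.12 = 0.98 at RR 1.5, 1.20/1.24 = 0.97 at RR 2 and 1.30/1.36 = 0.96 at RR 2.5.

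**The case against.** **The absence is shown for the protocol text only.** The list is introduced by the word *including*, the comorbidity and co-medication code files in Annex 2 cannot be read, and a separate analysis plan may exist. This limits certainty. But Annex 2 describes those files as codes to identify comorbidities, smoking and co-medications, not as a source of further covariates, and 5.6.2 already fixes what enters the score. If heart failure is in a file, naming it in 5.5 costs one line.

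**The listed variables already act as proxies.** ACE inhibitors, ARBs, thiazides, amiodarone, dronedarone, statins, antiplatelets and chronic kidney disease would jointly shrink a heart failure imbalance. This stands, and it is one reason to expect a modest bias. None of them is specific to heart failure, so the remaining imbalance is unknown until it is tabulated.

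**Misclassification and residual confounding are acknowledged.** The main outcome uses narrow terms, a broad definition will also be assessed, and 5.8 concedes residual confounding. Changing the code set does not balance work-up between arms, however, and the example given in 5.8 is a factor that cannot be recorded, whereas heart failure is a diagnosis that can be coded.

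**The fix may gain little.** In the mildest scenario it moves the factor only from 0.978 (25% versus 20%, RR 1.5) to 0.982 (24% versus 20%). This is correct. The gain is worthwhile only if the true imbalance is larger, which the plan as written would not reveal.

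**Stronger readings.** A reader might infer that heart failure imbalance determines who receives an ILD code, or that the omission would hide a DOAC signal. The documents support neither. They show no imbalance, no effect of heart failure on ILD coding and no direction. Even at 0.90, an illustrative true hazard ratio of 1.5 would become 1.35, which is attenuated but not hidden.

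**Conclusion.** The point holds in a limited form. Heart failure is not named in 5.5, so under 5.6.2 it is not directly matched on and its balance is not checked, while the outcome codes are unvalidated. It may bias the hazard ratio in either direction, chiefly in the AF stratum. On the assumed inputs the distortion is about 2% to 10% downwards, or about 2% to 12% upwards if heart failure is commoner with DOACs. This rests on three assumptions from outside the documents: that heart failure is linked to anticoagulant choice, that it raises the chance of an ILD code, and that the listed proxies leave a gap of 5 to 10 percentage points. The change is worth making because it is cheap and the study is meant to inform a regulator on a safety signal. It does not show that the planned result would be wrong.

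**What to change.** In 5.5 and 5.6.2, add baseline heart failure diagnosis and baseline loop diuretic prescription to the propensity score and to the SMD table, chiefly for the AF stratum. Report heart failure balance after matching, by database.

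Use recorded dyspnoea or cough, and prior chest imaging or respiratory referral, only in a sensitivity analysis in databases that hold them. The protocol does not show that all four capture these items, and the main adjustment set should be the same across countries before hazard ratios are pooled.

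The cost is a few more concept sets from records already in use and possibly slightly fewer matched pairs. No new data source is needed.

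### Coding smoking as current versus everything else means matching controls smoking only in part, and the balance check on that variable cannot show what is left

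*Protocol*

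**What the plan says.** Section 5.5 (Other variables) names smoking status among the baseline risk factors for ILD and concedes that "Smoking status may be missing". It then fixes the coding: "We will include current smoking status as a binary variable". A current smoker is coded 1. Everyone else is a "non-current smoker (0, i.e., other smoking status or the absence of a smoking status", the classification being made "based on the most recent smoking status prior to their index date".

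Section 5.6.2 carries this into the adjustment: "We will include the baseline risk factors and calendar year as predictor variables in the propensity score". Balance is judged variable by variable, "with SMD of less than 0.1 representing successful matching". Inverse probability weighting is the fallback if too few patients match, and no separate smoking definition is given for it.

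Section 5.6.4 adds that "No multiple imputation methods will be performed". The only sensitivity analysis, in section 5.6.6, concerns calendar time. Section 5.8 says in general terms that covariates may go unrecorded and that residual confounding is possible, but it does not mention the smoking coding.

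**The concern.** Three different groups share code 0: patients recorded as never having smoked, patients recorded as having stopped, and patients about whom nothing is recorded. A patient who stopped shortly before the index date is treated like a lifelong non-smoker. Two arms can therefore match perfectly on the coded variable and still differ in past smoking or in how often smoking was recorded.

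The planned diagnostics would not reveal this. Balance is assessed on each variable as coded, so the balance table could show smoking as successfully matched whatever the mix inside code 0. The same coding serves every database, drug and indication. If the hidden difference ran the same way in all four databases, the meta-analysis would not average it out.

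**Working it through.** The protocol states no smoking prevalence, no share of missing records, no risk ratio for smoking and no expected hazard ratio, so there is no figure of its own to reproduce. What follows is an illustration.

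**From the protocol**
- Smoking is binary, and code 0 holds ex-smokers, never-smokers and patients without a record (section 5.5).
- The balance threshold is a standardised mean difference (SMD) of 0.1 (section 5.6.2).

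**Assumed**
- Ex-smokers make up a share p_D of code 0 among DOAC users and p_V among VKA users. The base case is 40% versus 30%, and also the reverse.
- The relative risk of ILD for ex-smokers against the rest of code 0 is RR = 1.5 or 2.0.
- Current smokers are 12% of each arm after matching (coded SMD = 0) and have the same RR.

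**Step 1: imbalance that the check does not see.** Hidden SMD = (p_D − p_V) / √{[p_D(1 − p_D) + p_V(1 − p_V)] / 2}.
- 40% versus 30%: 0.10 / √[(0.24 + 0.21)/2] = 0.10 / 0.474 = 0.21, about twice the threshold, while the coded variable shows 0.

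**Step 2: bias factor within code 0.** [1 + p_D(RR − 1)] / [1 + p_V(RR − 1)].
- RR 1.5: 1.20 / 1.15 = 1.043.
- RR 2.0: 1.40 / 1.30 = 1.077.

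**Step 3: bias factor in the whole matched cohort.** Average risk in an arm = 0.12·RR + 0.88·[1 + p(RR − 1)].

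| p_D vs p_V | RR 1.5 | RR 2.0 |
|---|---|---|
| 40% vs 30% | 1.236 / 1.192 = 1.037 | 1.472 / 1.384 = 1.064 |
| 30% vs 40% | 1.192 / 1.236 = 0.964 | 1.384 / 1.472 = 0.940 |
| 35% vs 30% | 1.214 / 1.192 = 1.018 | 1.428 / 1.384 = 1.032 |
| equal shares | 1.000 | 1.000 |

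A ten-point gap thus moves the hazard ratio by about 4% to 6% in either direction, a five-point gap by about 2% to 3%, and no gap leaves it unchanged. Wider assumptions widen the range: at RR 3.0, shares of 55% versus 40% give 2.208 / 1.944 = 1.136, and 40% versus 50% give 1.944 / 2.120 = 0.917.

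**Step 4: how much the binary term does achieve.** Suppose that before matching, current smokers are 10% of DOAC and 15% of VKA users, ex-smokers are 40% of both, and RR is 2.0 for both groups.
- Before matching: (1 + 0.10 + 0.40) / (1 + 0.15 + 0.40) = 1.50 / 1.55 = 0.968.
- After matching current smoking to 12.5% in both arms, ex-smokers as a share of code 0 stay at 0.40/0.90 = 0.444 and 0.40/0.85 = 0.471. The factor becomes (1.125 + 0.875 × 0.444) / (1.125 + 0.875 × 0.471) = 1.514 / 1.537 = 0.985.

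In this example about half of the smoking bias is removed, so control is partial, not absent.

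**The case against.** The sponsor chose this coding openly. It says that smoking may be missing, defines the rule, and follows the same logic as section 5.6.4, where a condition counts as present if it is recorded. Recorded current smoking is in the propensity score. The score also contains "history of pneumonia, chronic obstructive pulmonary disease" and other covariates, and chronic obstructive pulmonary disease in particular may carry part of a patient's smoking history. Section 5.8 admits residual confounding. The smoking code list is an Annex 2 attachment whose content is not visible, so it is not known whether ex-smokers and never-smokers can be told apart in all four databases.

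Most of this stands, and it limits the consequence. A reader might infer that matching fails to control smoking altogether, or that every DOAC–VKA comparison is biased. The documents support neither: current smoking is balanced, past smoking has a partial proxy, and bias needs a difference between arms that nobody has yet measured. A reader might also infer that non-recording marks patients who are followed less closely and whose ILD is less often coded. That is possible, but the protocol does not show it. Nor does the protocol rank smoking above its other risk factors.

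Two things remain. The general limitation concerns information that is not recorded or cannot be included, whereas here a recorded status may be merged away. And nothing in sections 5.6.2 to 5.6.6 would let the study team find out whether the merging mattered.

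**Conclusion.** The point holds as a weakness of a stated coding rule: smoking is controlled in part, and the planned balance check cannot show the rest. Whether any bias results depends on the shares of ex-smokers and unrecorded patients in each arm after matching on the other covariates, and the protocol does not give them. On the assumed inputs, a ten-point gap in ex-smokers puts the hazard ratio off by about 4% to 6% either way, and equal shares put it off by nothing. The 4% to 8% obtained within code 0 should not be read as the bias in the overall hazard ratio, because balanced current smokers dilute it. With no expected hazard ratio in the protocol, this range cannot be set against a target effect. The change is worth making because it is cheap and makes a hidden imbalance visible, not because a bias has been shown.

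**What to change.** In section 5.5, replace the binary variable by four categories: current, ex, never and not recorded. Where a database does not separate ex from never, use three: current, recorded non-current and not recorded. Use the same categories in the propensity score for matching and, if it is used, for weighting. In section 5.6.2, ask for the SMD of each smoking category before and after matching, by database and indication, so that missingness is compared between arms as well.

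The cost is a sentence or two of text and three indicator terms in place of one (two with the three-category version). Slightly fewer patients may find a match. No imputation is needed and no patient is excluded for lack of a smoking record. One limit remains and should be stated in section 5.8: smoking history stays unknown within the not-recorded group, so balancing the size of that group does not guarantee balance inside it.

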5.5. Variables

Outcome:

The outcome of interest will consist of an incident diagnosis of ILD. ILD consists of a heterogeneous group of conditions. The ILD phenotype is therefore a composite of different codes representing ILD in general, or as specific conditions that are classed as an ILD. Exclusion of patients with pre-existing ILD will be evaluated using a composite phenotype consisting of any ILD related code. For the outcome in the analysis, a narrower definition of ILD will be used, namely pulmonary fibrosis, pneumonitis, ILD specific codes, and drug induced ILD (please see Appendix for exemplar codes lists). As codes for drug induced ILD are infrequently used, inclusion of this as a specific subgroup may provide limited information. We followed the "narrow" scope list of terms (i.e., very specific preferred terms) documented in the Introductory Guide for Standardised MedDRA Queries (SMQs) Version 25.0 [8]. We mapped these SMQ codes to SNOMED codes and used their OMOP concept IDs, and subsequently removed any codes that indicate another well-defined cause of ILD. Detailed list of codes included are shown in **Annex 2**.

Exposure:

Exposures of interest will consist of VKAs (comparator, consisting of either warfarin, acenocoumarol, phenindione, or phenprocoumon), and DOACs (target, consisting of apixaban, dabigatran, edoxaban and rivaroxaban). Exposures will be identified through prescriptions recorded in the electronic health record. Target exposures will be evaluated by class (any DOAC (direct oral anticoagulants)) and as individual drug substances.

For the on-treatment analysis, patients will be considered continuously exposed from cohort entry (index date) up to 30 days after the date of the last anticoagulant prescription in the patients record. In order to account for different treatment episodes over time, gaps of >90 days between anticoagulant prescriptions will be considered as different treatment episodes and continuous exposure will be censored 30 days after the last prescription before the gap. Detailed list of codes and terms included to identify exposure to DOACs are shown in **Annex 2**.

Other variables:

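### Cancer enters the propensity score with no split between recent and past disease, so recent cancer can stay unbalanced, chiefly in the VTE stratum, while every SMD passes

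*Protocol*

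**What the plan says.** Section 5.5 lists the baseline risk factors for the propensity score. Cancer appears in the run "history of sarcoidosis, history of cancer, exposure to medications", with no look-back window and no distinction between recent and past disease. The medication list that follows includes "methotrexate, cyclophosphamide, dronedarone". On cancer treatment more widely it says: "Information on prior radiotherapy and chemotherapy may not be available for some patients but will be included in the analysis when available". It also sets some factors aside: "Risk factors that will not be reliably identifiable include environment and occupational exposures, family history, and biologics"; these are not used in the analysis.

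Section 5.6.4 fixes how gaps are read: the analysis assumes that "an individual has a condition or prescription exposure if it is recorded in their electronic health record", and there is no multiple imputation. In effect, a treatment that was not recorded is analysed as a treatment not given.

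Section 5.6.2 matches 1:1 within indication on these factors plus calendar year and takes an SMD below 0.1 on each variable as success. The fallback, inverse probability weighting, is introduced with no further covariates.

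The narrow outcome in Section 5.5 is described as "namely pulmonary fibrosis, pneumonitis, ILD specific codes, and drug induced ILD", after removal of codes that point to another well-defined cause of ILD.

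**The concern.** A single history flag gives the same value to a cancer diagnosed last month and to one treated many years ago. Two arms can carry the flag equally often and still differ in how many patients have recent cancer. The covariates that could separate these patients are partial: chemotherapy and radiotherapy are used only where recorded, two named drugs cover only some treatments, and biologics are absent. The SMD table can show imbalance only in variables that have been built.

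This matters if recent cancer is related both to the choice of anticoagulant and to later pneumonitis or fibrosis codes. Both links are assumptions here; the protocol neither states nor excludes them. The VTE stratum is the natural place to worry, since cancer may be the reason for the thrombosis there, and the VTE hazard ratios are estimated and reported separately.

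Nothing else in the plan closes the gap. The exclusions in Section 5.3 cover mechanical valve, mitral stenosis and prior ILD. The sensitivity analysis in Section 5.6.6 concerns calendar time. The narrow and broad outcome definitions in Section 5.8 address misclassification of ILD, not confounding. Because the study is meant to inform a safety signal, a moderate bias in either direction could create or mask one.

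**Working it through.** The protocol gives no cancer prevalence, event count or power figure, so there is no stated number to reproduce. The calculation below shows only whether the mechanism can pass the planned check and how large it could be.

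**Assumed inputs (none from the protocol).** The cancer flag is 20% in both matched arms. Recent cancer is 8% in one arm and 4% in the other, i.e. 40% and 20% of flagged patients. The rate ratio R of an outcome code with recent cancer against without is 3, 5 or 10. The true drug effect is null.

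**Step 1: what the balance check sees.** For a binary covariate, SMD = |p1 − p0| / √{[p1(1 − p1) + p0(1 − p0)] / 2}.

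- Flag, 20% vs 20%: SMD = 0, passes.
- Recent cancer, 8% vs 4%: 0.04 / √[(0.0736 + 0.0384)/2] = 0.169. This would fail the 0.1 limit, but it is not tabulated.

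**Step 2: effect on a null hazard ratio.** For a rare outcome, with p1 in the DOAC arm and p0 in the VKA arm, HR = [1 + p1(R − 1)] / [1 + p0(R − 1)].

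| Recent cancer, DOAC vs VKA | R = 3 | R = 5 | R = 10 |
|---|---|---|---|
| 8% vs 4% | 1.16/1.08 = 1.07 | 1.32/1.16 = 1.14 | 1.72/1.36 = 1.26 |
| 4% vs 8% | 0.93 | 0.88 | 0.79 |
| 6% vs 4% | 1.12/1.08 = 1.04 | 1.24/1.16 = 1.07 | 1.54/1.36 = 1.13 |
| 4% vs 4% | 1.00 | 1.00 | 1.00 |

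Over a wider grid (flag 10% to 30%, recent share 30% to 50% in the DOAC arm vs 20% in the VKA arm, R from 2 to 10), the result runs from 1.03/1.02 = 1.01 to 2.35/1.54 = 1.53.

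**Step 3: can incomplete treatment records hide the imbalance?** Suppose true chemotherapy use is 8% vs 4% (SMD 0.169) and recording is equally incomplete in both arms.

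- 30% recorded: 2.4% vs 1.2%, observed SMD 0.090, passes.
- 50% recorded: 4% vs 2%, observed SMD 0.117, fails.

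So under-recording can hide the imbalance, but only when it is heavy.

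**Step 4: what a separate covariate would leave.** With recent cancer tabulated and held to SMD below 0.1, and 4% in the VKA arm, the largest DOAC prevalence that passes is about 6.2%. The null HR is then at most 1.04, 1.08 or 1.15 for R = 3, 5 or 10, against 1.07, 1.14 or 1.26 in Step 2.

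**The case against.** The case on the other side is substantial, and much of it stands.

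- A reader might infer that cancer is adjusted for only through a lifetime flag. The text does not support this. No look-back is given, whereas the ILD exclusion in Section 5.3 states expressly that it covers the whole prior history. The covariate code lists in Annex 2 are embedded files that cannot be read here. Nor is the flag alone: cyclophosphamide, methotrexate and recorded chemotherapy and radiotherapy are also included. What stands is that the visible text makes no recent/past split.
- Codes naming another well-defined cause of ILD were removed from the outcome. This may take out radiation-specific codes and so narrow the pathway. Unspecified pneumonitis and fibrosis codes remain within the stated definition, but the list cannot be checked.
- The documents give no evidence that recent cancer differs between arms, before or after matching. Age, smoking, calendar year and recorded treatment may already absorb part of any difference.
- The formula holds baseline prevalence constant over follow-up. If patients with recent cancer die or leave early, their share of person-time falls and the bias shrinks.
- A tabulated SMD is not a complete safeguard: 6% vs 4% gives 0.02 / √[(0.0564 + 0.0384)/2] = 0.092 and would pass. The gain comes mainly from matching on the variable.
- A primary care code date is an imperfect marker. A recent code may be a follow-up entry, and hospital-treated cancer may have no recent code.
- Section 5.8 admits residual confounding in general terms.

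The last point does not dispose of the matter. The examples in Section 5.8 are factors that cannot be included or are unknown. Recency of a recorded cancer can be approximated from dated records, which the plan already uses: a one-year window for the indication, and the most recent status before index for smoking.

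**Conclusion.** The point holds as a cheap improvement in confounding control, not as a contradiction or a wrong figure. The plan does not separate recent from past cancer, its treatment covariates are partial by its own account, and its balance check cannot show what is left.

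The possible size is modest to material: 1.07 to 1.26, or 0.93 to 0.79 with the imbalance reversed. It rests wholly on the assumed 20% flag, the 8% vs 4% split and rate ratios of 3 to 10. At a rate ratio of 3 the distortion is about 7% either way. With equal shares it is zero.

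A reader might go on to infer that the VTE hazard ratios will be biased, or that the bias favours one arm. The documents do not support either statement: they contain nothing on the distribution of recent cancer by anticoagulant.

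**What to change.** In Section 5.5, replace the single flag by three levels based on record date: no cancer code; last cancer code more than 365 days before index; cancer code within 365 days up to index. State the look-back for the older level. Use these levels in the propensity score and report their SMDs by indication and database.

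In Section 5.6.6, add a repeat of the VTE contrasts that excludes patients with a cancer code in the 365 days up to index.

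In Section 5.8, say that primary care code dates mark active cancer imperfectly and that some residual imbalance may remain.

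The cost is one recoded covariate and one repeat run, using the existing cancer code list and no new data source. The repeat run will have fewer VTE pairs and therefore wider intervals.
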